12.0 CRITERIA FOR REMOVAL FROM STUDY

Discontinuation of Study Treatment Due to Adverse Events

If ZW25 is discontinued, the patient must be discontinued from the study. Study treatment should not be resumed in the case of the following treatment-related events.

- \geq Grade 3 cardiac event
- Other non-hematologic events of Grade 4 severity
- Failure to meet re-treatment criteria within one cycle due to insufficient recovery from a treatment-related toxicity. In such cases, continuation of study treatment may be considered for those patients who have experienced clinical benefit if agreed upon by the Principal Investigator.

Removal of the Patient from the Study or from Study Drug Administration

The patient or legally authorized representative is free to withdraw consent and discontinue participation in the study at any time without prejudice to further treatment.

Patients will be removed from the study treatment when their disease worsens, and there is no clinical benefit. Additionally, a patient's participation in the study may be discontinued at any time at the discretion of the Investigator. The following may be justifiable reasons for the Investigator to remove a patient from the study:

- The patient suffers an intolerable adverse event
- Non-compliance, including failure to appear at one or more study visits
- The patient was erroneously included in the study
- The study is terminated.

If a patient or the patient's legal guardian(s), acting on behalf of the patient, discontinues participation in the study, or the patient is discontinued by the Investigator, the reason for discontinuation must be captured in the eCRF. Any AEs experienced up to the point of discontinuation must be documented on the AE eCRF. All serious adverse events (SAEs), and those AEs assessed by the Investigator as at least possibly related to study drug should continue to be followed until they resolve or stabilize, whichever comes first.

13.0 CRITERIA FOR OUTCOME ASSESSMENT AND ENDPOINT EVALUABILITY

13.1 Criteria for Therapeutic Response/Outcome Assessment

RESPONSE DEFINITION (RECIST 1.1)⁴⁸

DEFINITIONS:

Baseline: Baseline is defined as the most recent assessment performed prior to the first dose of study treatment. Baseline assessments must be performed within the period defined in the protocol eligibility criteria.

Memorial Sloan Kettering Cancer Center
[name]
[name]

Measurable Lesions: Except for lymph nodes (described below), measurable lesions are defined as those that can be accurately measured in at least one dimension (longest diameter to be recorded) as ≥ 10 mm with CT scan (if CT scans have slice thickness greater than 5 mm, the minimum size of a measurable lesion is twice the slice thickness).

- To be considered pathologically enlarged and measurable, a lymph node must be ≥ 15 mm in short axis when assessed by CT scan (CT scan slice thickness recommended to be no greater than 5 mm). At baseline and in follow-up, only the short axis will be measured and recorded.
- MRI may be substituted for contrast-enhanced CT for lesions at some anatomical sites, but not for lesions in the lungs. The minimum size for measurability is the same as for CT (10 mm) as long as the scans are performed with slice thickness of 5 mm and no gap. If MRI is performed with thicker slices, the size of a measurable lesion at baseline should be twice the slice thickness. In the event there are inter-slice gaps, this also needs to be considered in determining the size of measurable lesions at baseline.

Non-measurable lesion: all other lesions (or sites of disease) including small lesions (longest diameter <10 mm or pathological lymph nodes with ≥ 10 to < 15 mm short axis), are considered non-measurable.

- Lymph nodes that have a short axis < 10 mm are considered non-pathological and are not to be recorded or followed.
- Bone lesions, leptomeningeal disease, ascites, pleural/pericardial effusions, lymphangitis cutis/pulmonitis, inflammatory breast disease, and abdominal masses (not followed by CT or MRI), are considered as non-measurable.

Target lesions:

All measurable lesions up to a maximum of 2 lesions per organ and 5 lesions in total, representative of all involved organs, are to be identified as target lesions and measured and recorded at baseline.

- Target lesions are to be selected on the basis of their size (lesions with the longest diameter) to represent all involved organs, and to be those that lend themselves to reproducible repeated measurements.
- It may be the case that on occasion, the largest lesion does not lend itself to reproducible measurement in which circumstance the next largest lesion which can be measured reproducibly should be selected.

Memorial Sloan Kettering Cancer Center
[name]
[name]

- Target lesions will be measured at each assessment (longest axis for non-nodal lesions, shortest axis for measurable malignant nodal lesions).

Non-target lesions: All other lesions (or sites of disease) including all non-measurable lesions (including pathological lymph nodes with ≥ 10 to < 15 mm short axis) and all measurable lesions over and above the 5 target lesions are to be identified as non-target lesions and recorded at baseline.

- Measurements of these lesions are not required, but the presence, absence, unequivocal progression of each is to be recorded throughout follow-up.
- Lymph nodes that have a short axis < 10 mm are considered non-pathological and are not to be recorded or followed.

Special Considerations

Clinical Examination of Lesions: Superficial or visible lesions that cannot be assessed by CT scan or MRI will only be considered for response assessment if these lesions are biopsy-proven metastatic lesions and ≥ 10 mm in diameter. These lesions will be considered non-measurable and thus non-target for response assessment.

Cystic lesions: Cystic lesions thought to represent cystic metastases can be considered as measurable lesions if they meet the definition of measurability described above. However, if non-cystic lesions are present in the same patient, these are preferred for selection as target lesion.

Bone lesions: Bone scan, PET scan or plain films are not considered adequate imaging techniques to measure bone lesions. However, these techniques can be used to confirm the presence or disappearance of bone lesions.

- Lytic bone lesions or mixed lytic-blastic lesions, with identifiable soft tissue components, that can be evaluated by cross-sectional imaging techniques such as CT or MRI can be considered as measurable lesions if the soft tissue component meets the definition of measurability described above.
- Blastic bone lesions are non-measurable.

Lesions with prior local treatment: Lesions situated in a previously irradiated area, or in an area subjected to other locoregional therapy, are usually not considered measurable; however, if they meet the following criteria, they may be considered for study:

- there has been prior documented progression in the lesion by at least 2 sequential CT or MRI scans performed after the completion of radiation, or

- histopathological evidence of progression

Additionally, if such lesions meet the criteria for measurability, they may be considered target lesions.

Imaging Methods:

The same method of assessment and the same technique used to characterize each identified and reported lesion at baseline should be used during each follow-up assessment. Imaging-based evaluation is preferred to evaluation by clinical examination unless the lesion(s) being followed cannot be imaged but are assessable by clinical exam (referring to biopsy-proven visible lesions(s) at the vaginal apex).

Chest X-ray: Lesions that are identified on chest X-ray must be confirmed and followed by CT scan. If there is/are pre-existing chest lesion(s) before the baseline tumor assessment, a chest X-ray is not necessary to assess those lesions. The pre-existing chest lesion(s) must be assessed at baseline and followed by CT scans.

Conventional CT or MRI: This guideline has defined measurability of lesions on CT scan based on the assumption that CT slice thickness is 5 mm or less. If CT scans have slice thickness greater than 5 mm, the minimum size for a measurable lesion is twice the slice thickness. MRI is also acceptable in certain situations (e.g., for body scan) except for lung.

Other methods of assessment, PET-CT, ultrasound and FDG-PET should not be used for response assessment in this study.

Time Point Assessments:

Patients will have tumor measurements performed within 28 days prior to baseline and every 8 weeks through Week 24 and then every 12 weeks after 24 weeks, per RECIST 1.1 guidelines.

At baseline, tumors and lymph nodes are classified and documented as target or non-target per the definitions provided above. It is possible to record multiple non-target lesions involving the same organ as a single item (e.g., 'multiple liver metastases').

At all post-baseline evaluations, the baseline classification (target, non-target) is to be maintained and lesions are to be documented and described in a consistent fashion over time (e.g., recorded in the same order on source documents and CRFs).

For target lesions, measurements should be taken and recorded in metric notation. All tumor measurements must be recorded in millimeters.

At each assessment, a sum of the diameters (longest for non-nodal lesions, short axis for nodal lesions) for all target lesions will be calculated and reported. The baseline sum of the longest diameters (SLD) will be used as reference to further characterize any objective tumor regression in the measurable dimension of the disease. The lowest SLD (nadir) since, and including, the baseline value will be used as reference for evaluating progression.

After baseline, the actual size of the target lesion should be documented, if possible, even if the lesions become very small. If in the opinion of the radiologist, the lesion has likely disappeared, 0 mm should be recorded. If the lesion is present but too small to measure, an indicator of "too small to measure" will be provided on the CRF (a default value of 5 mm will be imputed during analysis).

Non-target lesions are to be assessed qualitatively (present, resolved, or unequivocal progression) and new lesion, if any, are to be documented separately.

At each evaluation, a time point response is to be determined for target lesions, non-target lesions, new lesions and overall.

Time Point Response Criteria

Target Lesion Time Point Response (TPR)	
Complete Response (CR)	Disappearance of all target lesions. All pathological lymph nodes (whether target or non-target) must have reduction in short axis to < 10 mm.
Partial Response (PR)	At least 30% decrease in the SoD of target lesions, taking as reference the baseline SoD
Progressive Disease (PD)	At least a 20% increase in the SoD of target lesions, taking as reference the smallest (nadir) SoD since and including baseline. In addition to the relative increase of 20%, the SoD must also demonstrate an absolute increase of at least 5 mm.
Stable Disease (SD)	Neither sufficient shrinkage to qualify for PR nor sufficient increase to qualify for PD.
Not Applicable (N/A)	No target lesions identified at baseline

Unable to Evaluate (UE)	One or more target lesions are not imaged and the remainder of the SoD compared with the nadir SoD does not meet the criteria for PD

If the target lesion for a patient meets the criteria for both PR and PD at a given time point, the target lesion response is PD.
 
If the nadir SoD is 0 (i.e., the patient had a prior target lesion CR), the re-appearance of any prior target lesions to any degree constitutes PD.
	
Non-Target Lesion TPR	
Complete Response (CR)	Disappearance of all non-target lesions and normalization of tumor marker level if tumor marker at baseline is above the upper normal limit. All lymph nodes must be non-pathological in size (< 10 mm short axis)
Progressive Disease (PD)	Unequivocal progression of non-target lesions. Unequivocal progression should not normally trump target lesion status. It must be representative of overall disease status change, not a single lesion increase.
Not Applicable (N/A)	No non-target lesions identified at baseline
Unable to Evaluate (UE)	One or more non-target lesions are not imaged and the remaining non-target lesions do not meet the criteria for PD

If the target lesion for a patient meets the criteria for both PR and PD at a given time point, the target lesion response is PD.
 
If the nadir SoD is 0 (i.e., the patient had a prior target lesion CR), the re-appearance of any prior target lesions to any degree constitutes PD.
	

New Lesion TPR	
Yes	Lesion present at follow-up visit either for the very first time or re-appearing (i.e., lesion was present at baseline, disappeared at a follow-up visit and re-appeared later).
No	No new lesions present at follow up

Unable to Evaluate (UE)	Patient non-assessed or incompletely assessed for new lesion
-------------------------	--

Determining Overall TPR

Target Lesion TPR	Non-Target TPR	New Lesions TPR	Overall TPR
CR	CR or NA	No	CR*
CR	Non-CR/non-PD	No	PR*
CR	UE	No	PR*
PR	Non-PD or NA or UE	No	PR*
SD	Non-PD or NA or UE	No	SD
UE	Non-PD	No	UE
PD	Any	No or Yes or UE	PD
Any	PD	No or Yes or UE	PD
Any	Any	Yes	PD
NA	CR	No	CR*
NA	Non-CR/non-PD	No	Non-CR/non-PD
Non-PD	Non-PD	UE	UE

CR, complete response; PR, partial response; SD, stable disease; PD, progressive disease; UE, unable to evaluate; NA, not applicable (no such lesions at screening); Any, CR, PR, SD, PD, NA or UE.

The overall response at a given time point does not depend upon the overall response assigned at any prior time point.

*Patients with an overall response of CR or PR must have a repeat tumor assessment performed no less than 4 weeks after the criteria for response are first met

Confirmation - The main goal of confirmation of objective response is to avoid overestimating the observed response rate. For patients with an overall response of PR or CR a given time point, changes in tumor measurements must be confirmed by repeat assessments that should be performed no less than 4 weeks after the criteria for response are first met. However, the presence or absence of confirmation is not considered when assigning a time point response.

Best Overall Response - Best overall response, incorporating confirmation requirements, will be derived during statistical analysis from the series of time point responses and need not be considered when assigning response at any time point.

13.2 Criteria for Study Endpoint Evaluability

Patients who have consented to the study and who have received at least one dose of study treatment will be considered enrolled and evaluable. Those patients who've consented but did not successfully complete the screening process and did not receive a dose of ZW25 will be considered a screen failure. Patient numbers for patients who screen fail will not be re-issued.

14.0 BIOSTATISTICS

14.1 Populations for Analyses

All treated population: all treated patients regardless if they completed cycle 1 or the amount of drug received.

Efficacy population: All treated patients except patients without a post baseline assessment of response will be excluded.

Sample Size

This study aims to assess the activity of ZW25 in advanced HER2 overexpressing endometrial cancers and carcinosarcomas as measured by the best overall response rate as determined by RECIST 1.1. Assuming we use a binary endpoint of response, defined as best overall response of CR or PR versus not (best overall response \leq 24 weeks from the start of treatment), a sample size of 25 patients provides 90% power to test the hypothesis that the response rate is promising (defined as 30% or higher) against a non-promising rate of 10% or lower. This calculation is based on historical data from studies with ineffective agents in a similar patient population, which have ORR $<$ 10% and PFS rate at 6 months $<$ 20%,^{7,49-51} and uses a two-stage minimax Simon design, with Type I error=10%. Sixteen patients will be enrolled in the first stage and if 1 response is observed among the 16 the study will end for lack of activity. If \geq 2 responses out of 16 are observed, the study will continue to stage 2, where an additional 9 patients will be enrolled for a total of 25. At the end of the study, if at least 5/25 responses are observed then this will be considered a positive study (i.e. conclude that ORR is $>$ 10%).

Based on historical accrual rates in similar populations, and with the increased prior lines of therapy that will not be allowed for eligibility, we anticipate successful enrollment of 2 patients per month yielding a total accrual time of 18 months. Accrual will continue until 25 evaluable for efficacy response patients are treated (i.e. 25 patients in efficacy population as defined above).

Sensitivity analysis for ORR will include in the calculation of ORR patients who do not have post baseline assessment of response as failures.

All statistical analyses will be performed using the most recently released version of SAS statistical software, unless otherwise noted. For categorical variables, the number (n) and percent of each category within a parameter will be presented. For continuous variables, the sample size (n), mean, median, and standard deviation, as well as the minimum and maximum values, will be presented. Missing data will not be imputed unless otherwise stated. There will be a detailed description of patient disposition, patient demographics, and baseline characteristics.

We will report the following statistics for the secondary objectives:

- The clinical benefit rate (CBR) of ZW25 therapy, defined as the percentage of patients with complete response (CR) + partial response (PR) + stable disease (SD) ≤24 weeks from the start of treatment will be reported and the 90% confidence interval will be estimated using exact binomial proportions
- Progression free survival (PFS), defined as the duration of time from start of treatment to time of recurrence, progression, or death due to any cause, whichever occurs first will be reported. Patients will be censored at last follow up date. The Kaplan Meier estimate of median PFS will be reported.
- Overall survival is defined as the duration of time from start of treatment to time of death due to any cause. Patients who are alive will be censored at last follow up date. The Kaplan Meier estimate of median OS will be reported.
- The duration of response (DOR) of ZW25 therapy, defined as the time from which measurement criteria are met for CR or PR (whichever status is recorded first) until the first date of documented disease progression, will be estimated using the Kaplan Meier method. Patients without documented progression will be censored at last follow up.
- Adverse events by the current version of Common Terminology Criteria for Adverse Events version 5 (CTCAE v5) will be tabulated in order to assess the safety profile and tolerability of ZW25therapy in patients with recurrent/persistent endometrial cancer.

ADA titers are a continuous variable and these will be assessed descriptively for changes over time as part of exploratory aims.

All patients will have their tumors molecularly profiled using the MSK-IMPACT platform, to evaluate for genomic alterations defined by MSK-IMPACT. Testing will (looking for presence/absence of genes at baseline and at end of study) be correlated to objective responses outcomes (binary covariates of CR or PR versus not) in an exploratory manner. Chi square or Fishers' exact test will be used to test this association. A subset analysis of patients who respond and then progress and have post progression material for molecular profiling will be performed in order to determine the mechanism(s) underlying acquired resistance. Specifically, we will be looking for presence of genetic alterations (at progression compared to baseline) which based on their understood biological mechanism may explain

acquired resistance. This analysis will be descriptive with the intention of understanding genetic alterations over time (at progression) and the types of mutation alterations among patients who respond and then progress. Patients will be followed up for a minimum of 12 months. Most variables above are binary (presence/absence) or expressed (yes/no) and they will be tested for association with response (yes/no) using Chi square or Fishers' exact test.

Serial pre- and post-treatment blood samples will be collected for cell-free tumor DNA analysis and sequenced using continuous quantitative methods (digital droplet PCR or hybridization capture next-generation sequencing) for the Rb, CD-K, PI3K- pathway alterations identified by pre-treatment and post-treatment tumor testing and descriptively correlated to clinical outcome. Binary covariates (presence/absence) will be tested for association with response (binary: CR or PR vs not) using Chi square of Fishers' exact test. Circulating tumor DNA is a continuous variable and these will be assessed descriptively for changes over time as part of exploratory aims.

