4.2 Intervention

Up to 25 patients will be enrolled on this study and will receive the RP2D of ZW25 at 20mg/kg intravenously (IV) every two weeks.

The study will be conducted in two stages. Stage 1 will accrue 16 patients; if two or more responses are seen, study will proceed to Stage 2 which will accrue an additional 9 patients. In this study the recommended ZW25 dose will be 20mg/kg intravenously (IV) every two weeks. Treatment cycles will be 28 days long.

Patients will receive study treatment until disease progression, intolerable toxicity, elective withdrawal from the study, study completion, or study termination. Patients will continue to receive study treatment until they present with progressive disease (PD) per Response Evaluation Criteria in Solid Tumors (RECIST) version 1.1, develop unacceptable toxicity or withdraw consent, whichever comes first, or until the study is terminated.

Tumor assessments, including radiological assessments by computerized tomography (CT) or magnetic resonance imaging (MRI) scans are performed at Screening and

Memorial Sloan Kettering Cancer Center
[name]
[name]

subsequently every eight weeks for the first 24 weeks and then every twelve weeks until PD, death or initiation of subsequent anti-cancer therapy, whichever occurs first.

Safety will be evaluated in this study through the monitoring of all serious and non-serious AEs, graded according to the current version of the National Cancer Institute Common Terminology Criteria for Adverse Events (CTCAE v.5).

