Patients who have consented to the study and have received at least one dose of study treatment will be considered enrolled and evaluable. Those patients who've consented but did not successfully complete the screening process and did not receive a dose of ZW25 will be considered a screen failure. Patient numbers for patients who screen fail will not be re-issued.

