Survival Status ⁿ												● ⁿ

- a. Within 28 days prior to the start of Cycle 1, Day 1
- b. Directed physical examination is acceptable while on study treatment. Full examination is required at screening and the EOT visit.
- c. Within 14 days prior to the start of Cycle 1, Day 1
- d. Vital signs (blood pressure, pulse, respiration rate, and temperature) will be measured as outlined in the full protocol.
- e. Day 1 laboratory assessments may be performed up to 4 days prior to study agent administration. Laboratory results must be reviewed prior to each scheduled administration of ZW25, with the exception of coagulation testing (PT/INR, aPTT). In the event of severe toxicity, laboratory tests must be repeated as necessary until the toxicity resolves or stabilizes.
- f. For WCBP, a urine or serum pregnancy test will be performed at screening, prior to dosing on Day 1 of every cycle (it can be performed up to 14 days prior to Day 1) and at the 30-day Follow-Up visit. Additional testing may be performed in accordance with institutional requirements or local regulation.
- g. Patients will complete tumor assessments every 8 weeks (from C1D1) until Week 24, then every 12 weeks (± 1 week). If a patient discontinues prior to documentation of PD, a tumor assessment is to be performed at the End of Study visit or 30-Day Follow up visit, if not performed within the previous 6 weeks. Patients who have discontinued study treatment for reasons other than PD will be followed per RECIST 1.1 every 12 weeks (±3 weeks) until documentation of PD, starting a subsequent anti-cancer therapy or for up to one year from Cycle 1, Day 1, whichever comes first.
- h. As clinically indicated.
- i. All AEs and SAEs from the time of informed consent should be recorded.
- j. ECOG assessment is not necessary on Cycle 1 Day 1 if screening assessment was performed within 3 days prior
- k. For logistical reasons such as holidays, a +/- 3 day window applies to all study visits.
- l. Mandatory biopsy at screening and EOT (at time of progression of disease) within 14 days of EOT before initiating new treatment regimen.
- m. Research bloods include ADA and cfDNA sample collection. Research bloods can be collected at screening or cycle 1 day 1 before initiating treatment for baseline collections.

ADA will be collected at baseline and pre-dose at cycles 2, 4, 6, 8, 12, 18, 24 Day 1.

- n. Survival status' can be documented with a phone call or any clinic visits.

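### Section 14.1 drops and replaces treated patients who have no post-baseline assessment, so the final 5/25 rule rests on a denominator that conflicts with Section 13.2 and can only raise the ORR

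*Combined protocol and SAP*

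**What the plan says.** Section 14.1 defines an all-treated population and a narrower efficacy population: "Efficacy population: All treated patients except patients without a post baseline assessment of response will be excluded". It sets the accrual target on the narrower one: "Accrual will continue until 25 evaluable for efficacy response patients are treated", with a parenthesis confirming that the 25 belong to the efficacy population. The final rule calls the study positive at 5 or more responses in 25. For the interim look it says only "Sixteen patients will be enrolled in the first stage", without naming a population. Unassessed patients return in one place: "Sensitivity analysis for ORR will include in the calculation of ORR patients who do not have post baseline assessment of response as failures".

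Elsewhere evaluability is defined differently. Section 13.2 says: "Patients who have consented to the study and who have received at least one dose of study treatment will be considered enrolled and evaluable". Section 7.0 gives the same definition in almost the same words. Section 4.2 sets the ceiling, as does Section 1.0: "Up to 25 patients will be enrolled on this study".

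On scans, the first scheduled post-baseline assessment is at week 8. For a patient who stops before documented progression, note g to the Section 11.0 schedule says "a tumor assessment is to be performed at the End of Study visit or 30-Day Follow up visit", unless one was done in the preceding 6 weeks. The schedule table itself marks the End of Treatment and 30-day scans with note h, which makes them dependent on clinical indication.

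**The concern.** The primary endpoint has two denominators. Under Sections 7.0 and 13.2 every dosed patient counts. Under Section 14.1 a dosed patient without a later scan is removed and replaced. With k such patients, filling the efficacy population takes 25 + k enrolled patients, so the cap of 25 fails as soon as k = 1.

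The direction of the effect is known. A patient with no post-baseline assessment cannot have a CR or PR, so x/25 is never smaller than x/(25 + k). Patients who die, deteriorate or leave before week 8 are the likeliest to be removed, and they would be failures in an all-treated analysis.

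The claim that the ORR exceeds 10% can therefore depend on which section is followed. The 2/16 gate has the same ambiguity: 16 + 9 = 25 points to assessed patients, while the definition of an enrolled patient points to treated patients.

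**Working it through.** **Inputs (Section 14.1).** Null rate 10%, promising rate 30%, Simon minimax design, type I error limit 10%, power 90%. Stage 1 has 16 patients and continues at 2 or more responses. Stage 2 adds 9, and success is 5 or more of 25. The unassessed share d is not given, so 5%, 10% and 20% are assumptions.

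**1. Reproduce the design.** P(success | p) = Σ over x ≥ 2 of P(X₁ = x; 16, p) × P(X₂ ≥ 5 − x; 9, p).

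- p = 0.10: 0.2745×0.0530 + 0.1423×0.2252 + 0.0514×0.6126 + 0.0170 = 0.0951
- p = 0.30: 0.0732×0.5372 + 0.1465×0.8040 + 0.2040×0.9596 + 0.5501 = 0.9030

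In each line the last term is P(X₁ ≥ 5). A search for the smallest qualifying design returns the same one (1/16, 4/25). The design arithmetic is sound.

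**2. Effect of the exclusion when the null is an all-treated rate.** Unassessed patients contribute no responses, so the rate among assessed patients is 0.10/(1 − d).

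- Reading A: both rules use assessed patients. Put p = 0.10/(1 − d) into the formula in step 1.
- Reading B: stage 1 counts the first 16 treated and the final rule counts 25 assessed. The number assessed in stage 1 is m ~ Bin(16, 1 − d), responses are Bin(m, 0.10/(1 − d)), and then 25 − m more assessed patients are added.

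| d (assumed) | 0.10/(1 − d) | Type I error, A | Type I error, B | Treated to reach 25 assessed, 25/(1 − d) |
|---|---|---|---|---|
| 0 | 0.100 | 9.5% | 9.5% | 25.0 |
| 5% | 0.105 | 11.2% | 11.0% | 26.3 |
| 10% | 0.111 | 13.3% | 12.8% | 27.8 |
| 20% | 0.125 | 19.0% | 17.2% | 31.3 |

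The 10% limit is crossed at d = 1.5% (A) or 1.7% (B). If the null is instead a rate among assessed patients and both rules use assessed patients, type I error is 9.5% at every d.

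**3. At the decision boundary.** As a gauge, the exact one-sided 90% lower bound (fixed sample, ignoring the interim) is 10.06% for 5/25 and 9.66% for 5/26. With exactly 5 responses, one excluded patient moves the bound below 10%. With 6 responses it stays above 10% up to 6/32 (10.16%) and falls below at 6/33 (9.84%).

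**4. The all-treated rule instead.** With 25 treated and unassessed patients as failures, type I error is 9.5% at an all-treated 10% and power is 90.3% at an all-treated 30%, whatever d is. If 30% was meant among assessed patients, the all-treated rate is 0.30(1 − d) = 0.285, 0.27 or 0.24, and power is 87.3%, 83.7% or 74.2%.

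**The case against.** The plan handles much of this. It defines both populations, prespecifies the ORR with unassessed patients as failures, and promises a full account of patient disposition, so a reader would see both figures. That reduces the risk of a misleading report. It does not settle the decision, because no threshold is attached to the sensitivity result and nothing says what follows if 5/25 passes and 5/26 does not.

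The inflation also depends on how the null is read. Section 14.1 ties the 25 to assessed patients, and the background data on this drug in Section 3.0 use response-evaluable denominators (15/48 and 14/34). Both favour a null among assessed patients, under which type I error does not move. This stands as a condition on the numbers. The same background shows the choice matters: 48 evaluable against 67 treated, and 34 against 43, although these were interim data and do not estimate the share here.

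The calculation sits at the edge of the null, whereas Section 14.1 describes historical rates below 10%. At an all-treated rate of 8%, reading A gives 5.3%, 6.4% and 9.5% for the three shares, never above 10%. At 9% it gives 7.9%, 9.5% and 13.9%. Type I error is properly judged at the boundary, but these figures show the practical inflation may be smaller. Likewise, 1.5% is less than half a patient in 25. The smallest share that can occur is about 1/26, roughly 4%, where reading A gives 10.9%.

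The lower bound in step 3 is not a protocol criterion, since success is defined by a count. Finally, note g, including its continued RECIST follow-up after stopping without progression, will keep some early leavers in the efficacy population. Given note h and the 6-week waiver, capture is not assured.

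**Conclusion.** The concern holds. The definitions of evaluability and the enrolment cap cannot all be met once one treated patient goes unassessed. The success rule is attached to the denominator that can only favour the drug, and the interim denominator is not stated. These points need no assumption.

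The size is conditional. With an all-treated null of 10%, type I error is about 11% to 19% for unassessed shares of 5% to 20%, against a design value of 9.5%. With a null among assessed patients and both rules on them, there is no inflation. The documents identify neither the null's denominator nor the likely share. The planned sensitivity analysis softens the problem without resolving it. This should be fixed before the rule is applied.

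**What to change.** In Section 14.1, make the all-treated population primary for both rules: the first 16 treated for the gate and 25 treated for the final test, with no post-baseline assessment counted as non-response. Move the efficacy population to the sensitivity analysis. Delete the sentence that extends accrual until 25 are evaluable. State whether the 10% and 30% rates refer to treated or assessed patients. Align Sections 1.0, 4.2, 7.0, 13.2 and 14.1.

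**Cost.** If 30% is an all-treated target, only wording changes: power stays at 90.3% with 25 patients, and the reported ORR may be slightly lower. If 30% was meant among assessed patients, either state the lower power in step 4 or enlarge the trial. Minimax designs restoring 90% power against an all-treated null of 10% are:

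- 5% unassessed: 31 treated (1/17, 5/31; type I error 8.0%, power 90.4%)
- 10% unassessed: 33 treated (3/26, 5/33; 9.9%, 90.3%)
- 20% unassessed: 47 treated (2/28, 7/47; 9.0%, 90.0%)

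If the sponsor prefers to keep the efficacy population primary, the minimum is to say that both rates are per assessed patient, name the stage 1 denominator, correct Sections 7.0 and 13.2 and the cap, and state what follows if the all-treated result disagrees. That removes the contradiction but leaves the reported ORR biased upward relative to all treated patients.
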